5.5.2.1. Sensitivity Analyses of Supplemental Estimand

A sensitivity analysis using control-based imputation will be conducted. The analysis will impute the binary primary endpoint for participants who received prohibited medications to treat

COVID-19 using PROC MI. Missing primary endpoint status through Day 29 will be imputed using monotone logistic regression as stated in the sensitivity analyses for the primary analysis but informed only by the placebo group. This will be implemented by the MNAR statement with the option MODELOBS =(TRT=0), where TRT=0 indicates the placebo group.

5.5.3. Key Secondary Endpoints and Analyses

[Appendix H](#) provides an overview of the main estimation and sensitivity analyses for the key secondary estimands (Estimand 2 and Estimand 3).

To control the overall type I error rate at .05 (2-sided), a hierarchical testing procedure will be used, such that testing for the key secondary analyses difference will proceed only if the treatment difference is statistically significant in the primary analysis.

The key secondary endpoints will be tested in the following order:

1. Severe/critical COVID-19 or all-cause death through Day 29
2. COVID-19-related emergency room visit, COVID-19-related hospitalization, or all-cause death through Day 29
3. Time to sustained resolution of COVID-19 symptoms through Day 29

For binary endpoints, the analysis will use the same methodology as the primary efficacy endpoint for determining a standardized estimator for a binary outcome (standardized risk difference/standardized relative risk reduction) with adjustment for the following prognostic factors: age (continuous), sex (categorical), baseline serostatus (categorical as positive; negative), BMI (continuous) and baseline viral load (continuous as \log_{10} copies/mL) and will be conducted on the mFAS-non-Omicron analysis set. Similar to the primary analysis, the standard error of the standardized estimator will be estimated using the delta method.

For the first key secondary endpoint, if the determination of investigator assessment of COVID-19 severity is missing at a visit, it will be imputed as not severe/critical COVID-19 (or all-cause death) unless the participant is hospitalized due to COVID-19 at the time of the visit. In this case, the assessment of COVID-19 severity will be imputed as severe/critical COVID-19.

For the second key secondary endpoint, missing data will be imputed as not having a COVID-19-related emergency room visit, COVID-19-related hospitalization, or all-cause death through Day 29. The number and percentages of participants who experience the event and do not experience the event will be summarized by treatment group, including summaries of missing data, and each component of the endpoint. The observed risk difference (placebo minus ADG20) with 95% CI (using the Miettinen-Nurminen method), observed relative risk reduction, standardized risk difference between the ADG20 arm and placebo arm with 95% CI and associated p-values, and standardized relative risk reduction with 95% CI will be provided.

Time to sustained resolution in COVID-19 symptoms through Day 29 will be analyzed by KM methodology and stratified Cox Proportional Hazard model. Survival curves between ADG20 and placebo will be compared using a log-rank test stratified by age (categorical as 12-17, 18-65, and >65 years). A stratified Cox Proportional Hazard model will be used to estimate the hazard ratio where the model includes age (categorical as 12-17, 18-65, and >65 years) as stratification variable and sex (categorical), baseline serostatus (categorical), baseline BMI (continuous), and

baseline viral load (continuous as \log_{10} copies/mL) as covariates. Comparison of the survival distributions will use the score test for the hazard ratio from the Cox model.

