7.4. Statistical Analyses

Statistical analysis will be performed using SAS software Version 9.4 or later. Continuous variables will be summarized using the mean, standard deviation, median, first and the third quartiles, minimum value, and maximum value. Categorical variables will be summarized using frequency counts and percentages. Data will be listed.

The objectives and endpoints for all study phases are shown in [Table 2-1](#).

Unless otherwise specified, estimations involving the primary and secondary endpoints will follow a treatment policy strategy for the handling of intercurrent events, which uses and analyzes all data for the endpoints after the intercurrent event has occurred. When a hypothetical strategy is used, data may be censored in the case of a time to event endpoint or imputed in the case of continuous or binary endpoints.

Estimand attributes, intercurrent events of interest, and rationales for intercurrent event handling strategies for the primary and key secondary estimands will be fully described in the SAP. The main estimation for the primary efficacy and key secondary efficacy endpoints is described in [Section 7.6](#) and [Section 7.7](#). Definitions of censoring and details of imputation methodology will be provided in the SAP.

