Viral load >5 (\log_{10} copies/mL) on Day 7 (± 1) based on NP samples	Same as primary efficacy analysis (see Section 7.6). Analysis will be performed in mFAS-non-Omicron-NP with available data at Day 7. Analysis will be repeated using a second definition of high viral load (viral load $>4 \log_{10}$ copies/mL).

Endpoint	Statistical Analysis Methods
Duration of SARS-CoV-2 viral shedding from Day 1 through Day 29 assessed by RT-qPCR from saliva samples	KM methodology will be used to analyze duration of viral shedding from Day 1 through Day 29 by SARS-CoV-2 RNA defined as time from the first dose date to the first date the viral load is not detected, ie, below the limit of detection (LOD), and sustained through Day 29. KM curves will be compared between ADG20 and Placebo using a log-rank test stratified by age (categorical). A stratified Cox Proportional Hazard model will be used to estimate the hazard ratio where the model includes age (categorical as 12-17 years, 18-65 years and >65 years) as stratification variable and sex (categorical), baseline serostatus (categorical as positive; negative), baseline BMI (continuous) and baseline viral load (continuous as \log_{10} copies/mL) as covariates. Comparison of the survival distributions will use the score test for the hazard ratio from this Cox model. Analyses will be performed on the mFAS-non-Omicron-S. Deaths occurring prior to achieving cessation of viral shedding will be censored at Day 30.
Change from baseline in SARS-CoV-2 viral load (\log_{10} copies/mL) to Days 3, 5, 7, 11, 14, 21, and 29 assessed by RT-qPCR from saliva samples	Observed saliva baseline and post-baseline values are used to calculate change from baseline. Mixed model for repeated measures with treatment group and the prognostic factors (with observed saliva baseline) in the primary efficacy endpoint analysis as covariates will be performed. The LS mean for the point estimate in each group and 95% CIs will be presented. The difference in LS means between the ADG20 group and the placebo group and the 95% CIs for the differences will be determined. A plot of the LS means with 95% CIs by day assess by treatment group will be presented. The analysis will be performed on the mFAS-non-Omicron-S with available data at each timepoint. In addition, a two-sample t-test will be used to compare change from baseline viral load between treatment at each time point without covariate adjustment (unadjusted mean difference).

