1. INTRODUCTION

This SAP describes the planned analyses for ADG20-TRMT-001 (STAMP) based on the clinical study protocol, version 6.0, dated 02-Mar-2022. In addition to the information presented in the statistical analysis section of the protocol (Section 7), which provides the principal features of analyses for the study, this SAP provides statistical analysis details/data derivations. It also documents modifications or additions to the analysis plan that are not principal in nature and result from information that was not available at the time of protocol finalization.

The STAMP study is a randomized, double-blind, placebo-controlled, multi-center adaptive study of the safety, efficacy, PK, and antiviral activity of the mAb ADG20 in the treatment of ambulatory participants with mild or moderate COVID-19 with a high risk of disease progression based on age or co-morbid medical conditions. The study will be conducted in 2 phases with data review conducted by an iDMC throughout.

PPD Biostatistics and programming team, designee of Adagio Therapeutics, Inc., will perform the statistical analysis; SAS Version 9.4 or higher will be used. If the methods in this SAP differ from the methods described in the protocol, the SAP will prevail. Any additional analysis outside of the planned analysis following the Day 29 database soft lock or the final database lock that are not performed by PPD are not included in the SAP.

The STAMP study was impacted by the emergence and global spread of the SARS-CoV-2 B.1.1.529 (Omicron) variant, which was first detected in South Africa and Botswana in November 2021. In vitro assessments of the neutralization activity of ADG20 demonstrated markedly reduced activity against authentic Omicron virus compared with prior variants such that ADG20 is unlikely to demonstrate adequate efficacy against SARS-CoV-2 infections caused by the Omicron variant. As a result, enrollment the study was suspended on 11-Jan-2022 as Omicron had become or was likely to become the predominant variant in regions enrolling the trial.

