Time to sustained recovery (improvement or resolution) of COVID-19 symptoms through Day 29: Defined as the time from the first dose date to the earliest date when sustained improvement or sustained resolution of COVID-19 symptoms is met (as detailed below) through Day 29. COVID-19 symptoms assessed include fever, chills, cough, sore throat, congestion, shortness of breath/difficulty breathing at rest, shortness of breath/difficulty breathing with exertion, muscle or body aches, fatigue, headache, nausea, vomiting, and diarrhea. Loss of taste/smell is excluded from this analysis.

Time to sustained improvement of COVID-19 symptoms through Day 29: Defined as the time from the first dose date to the first date when all of the above symptoms are scored as moderate or severe at baseline are scored as mild or absent, all of the above symptoms scored as mild or absent at baseline are scored as absent, and with no symptom worsening or new symptoms, except for cough, fatigue, and headache which may be mild or absent, through Day 29.

Time to sustained resolution of COVID-19 symptoms through Day 29: Defined as time from the first dose date to the first date when all of the above symptoms are scored as absent with no symptom recurrence or new symptoms, except cough, fatigue, and headache which may be mild or absent, through Day 29.

Censoring rules for time to COVID-19 symptoms through Day 29 analysis:

- Participants who are randomized but not treated are censored at Day 1.

- Participants who have any COVID-19-related hospitalization (≥ 24 hours) or all-cause death through Day 29 (as defined in the primary endpoint) will be censored at Day 30.
- Participants who have not been followed through Day 29 visit (discontinuation from study or incomplete follow-up at the time of analysis) will be censored at the last contact date.
- Participants who have completed the Day 29 visit and do not experience a defined event through Day 29 will be censored at Day 30.

[Table 2](#) provides further programming details.

Table 2: Criteria for Sustained Improvement and Sustained Resolution of COVID-19 Symptoms Through Day 29

COVID-19 Symptoms	Baseline Severity	Criteria for Sustained Improvement	Criteria for Sustained Resolution

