4.2. Sample Size

The primary analysis is the comparison of the ADG20 arm versus the placebo arm with respect to proportion of participants infected with a non-Omicron variant of SARS-CoV-2 with a COVID-19-related hospitalization or all-cause death through Day 29.

The original required sample size was calculated based on the following assumptions obtained from a review of data from studies of other mAbs in participants with a high risk for disease progression leading to hospitalization or death prior to widespread emergence of both the Delta and Omicron variants ([AstraZeneca 2022](#); [Eli Lilly and Company 2022](#); [GlaxoSmithKline 2021](#); [Regeneron 2022](#)). The original sample size of 1084 participants was planned with 90% power, 2-sided alpha .05, and a 1:1 randomization ratio to detect a statistically significant risk reduction with a true efficacy of relative risk reduction 70% and a 5% event rate in the placebo arm.

At the time of enrollment suspension in January 2022, a total of 399 participants were randomized. Of them, approximately 320 participants will be included in the primary efficacy population of participants with a non-Omicron variant of SARS-CoV-2. Based on blinded monitoring of the primary endpoint outcomes, an aggregate event rate of approximately 9% was observed, indicating a higher placebo event rate than previously assumed and providing approximately 80% power to test the primary endpoint in the primary efficacy population given an estimated placebo event rate of 12% and the same efficacy assumption.

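### Does time to sustained symptom resolution, the last key secondary, need a rule saying which of its two tests decides?

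*SAP*

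**What the plan says.** SAP 4.4 and 5.5.3 control the overall two-sided type I error at .05 with a hierarchy opened by the primary endpoint. "The key secondary endpoints will be tested in the following order": severe/critical disease or death, then emergency visit, hospitalization or death, then time to sustained resolution. For the third endpoint, SAP 5.5.3 and Protocol 7.7 carry the same two statements:

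- "Survival curves between ADG20 and placebo will be compared using a log-rank test stratified by age", in three age bands.
- After describing an age-stratified Cox model with sex, serostatus, BMI and viral load as covariates: "Comparison of the survival distributions will use the score test for the hazard ratio from the Cox model".

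Neither test is called confirmatory, supportive or descriptive in Protocol 7.5, SAP 4.4, SAP 5.5.3 or SAP Appendices H and I. The appendices stop at Estimand 3, which is the second key secondary.

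The rest of the analysis is specified. Protocol 7.7 names the analysis set. Protocol 7.4 gives the default for intercurrent events: "Unless otherwise specified, estimations involving the primary and secondary endpoints will follow a treatment policy strategy for the handling of intercurrent events". SAP 3.5.1 gives the censoring rules; participants with a hospitalization or death ("as defined in the primary endpoint) will be censored at Day 30") stay in the risk set as unresolved. SAP Appendix F covers missing diary entries.

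**The concern.** A confirmatory step should have one p-value. Here the plan produces two. Had the Cox model contained treatment alone, its score test would match the stratified log-rank apart from tie handling and nobody need care. Four covariates break that identity, so one test can fall below .05 and the other above it. A team that saw both before choosing could pick the favourable one, and the size of the step would then exceed 5%. At stake is the claim on symptom resolution. The primary and the first two key secondaries come earlier in the hierarchy and cannot be affected.

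**Working it through.** **Do the texts rank the tests?** Vocabulary alone does not. Protocol Table 7-2 (viral shedding) says "KM curves will be compared between ADG20 and Placebo using a log-rank test stratified by age (categorical" and keeps the term survival distributions for the score test, but the matching row of SAP Table 4 uses that term for a log-rank test too. "If the methods in this SAP differ from the methods described in the protocol, the SAP will prevail" does not help either, because the documents agree on this endpoint. Structure helps more. The score-test sentence closes the description here and for the other time-to-event endpoints (Protocol 7.8; SAP Table 4, 5.5.6.2, 5.5.6.3). In the primary analysis (Protocol 7.6, SAP 5.5.1) an unadjusted risk difference is shown with its interval, while the named p-value belongs to the covariate-adjusted estimate. Unadjusted for display, adjusted for testing, is the consistent reading.

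**Why the p-values differ.** With treatment alone, the score at zero is the sum over strata and event days of d₁ − d·n₁/n, the log-rank numerator. With covariates z, n₁/n becomes a ratio of sums of exp(γ′z), with γ estimated.

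**The plan's own figures.** It gives none for this endpoint. The primary figures that set the gate do reproduce. Per-arm n = [1.960·√(2p̄q̄) + 1.282·√(p₁q₁ + p₂q₂)]² / (p₁ − p₂)². With 5% versus 1.5% this is 538, total 1,076, against 1,084 stated (power at 1,084 is 90.2%). SAP 4.2 bases the current power on 320 participants, "given an estimated placebo event rate of 12% and the same efficacy assumption": 12% × 0.30 = 3.6%, and 160 per arm gives 80.3%, against about 80% stated.

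**Simulated tests.** Inputs from the documents: 320 participants, 1:1 allocation, daily times, censoring at Day 30. Everything else is assumed.

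- Simulation A censors primary events at Day 30: 9% in both arms under the null, 12% versus 3.6% otherwise. Placebo median is 14 days among the rest. Log hazard ratios for sex, serostatus, BMI per SD and viral load per SD are 0,0,0,0 (none); 0.1, 0.2, −0.1, −0.15 (weak); 0.2, 0.5, −0.2, −0.3 (moderate); 0.4, 0.8, −0.3, −0.6 (strong). Ranges cover two tie methods.
- Simulation B has about 65% resolved by Day 29, no separate primary events, and log hazard ratios 0.3, 0.5, −0.2, −0.4 multiplied by 0, 0.5, 1 and 1.5.

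Size of each test alone: log-rank 4.7% to 5.2% (A), 4.6% to 4.9% (B); Cox score 4.5% to 5.9% (A), 4.2% to 5.1% (B).

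| Covariate effect | none | weak | moderate | strong |
|---|---|---|---|---|
| Null, either test significant, A | 5.1–5.5% | 6.0–6.1% | 6.3–6.9% | 8.0–8.5% |
| Null, either test significant, B | 5.5% | 6.0% | 6.7% | 7.1% |
| Tests disagree, HR 1.2, A | 4% | 6% | 11–12% | 20–21% |
| Tests disagree, HR 1.35, A | 2% | 3% | 6% | 13–14% |
| Tests disagree, HR 1.35, B | 3.2% | 7.7% | 15.3% | 23.7% |

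The null rows treat the step as if it stood alone.

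**With the gate.** In A's null the primary null is also true, so any false claim on resolution needs a false primary claim first, and familywise error stays at the primary's 5% or so. A rerun of that setting (2,500 trials per scenario; none, moderate, strong; standard error about 0.2 points) gave:

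- primary and either test significant: 0.8%, 1.1%, 0.9%
- primary and Cox score significant: 0.7%, 0.9%, 0.7%

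The differences are 0.1, 0.2 and 0.2 points, before key secondaries 1 and 2 are also required.

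**When the gate usually opens.** With 12% versus 3.6%, an arm gap of 12 − 3.6 = 8.4 points is censored as unresolved, so the resolution endpoint is not null even at HR 1.0 among the rest: the log-rank rejected in 21% to 22% of trials and the Cox score test in 21% to 26%.

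**The case for a change.** The strongest case for a change is that no passage states which p-value decides, that Protocol 7.7 promised full estimand attributes in the SAP while the appendices omit this endpoint, and that one sentence would close the matter. The plan itself calls the covariates prognostic, so the no-effect column is not its own expectation and real disagreement is possible.

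The textual part stands: the label is missing. The part about error control mostly does not. Inflation needs a rule under which either test counts, or a choice made after unblinding. The plan contains no such rule, and SAP 3.2 bars such a choice. One scenario is left open. If the primary effect were real and exactly offset by slower resolution among the remaining participants, the gate would open on a true null and the rates for the step taken alone would be the relevant ceiling. Nobody simulated that, and it would still need the either-counts rule.

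**Conclusion.** No change to the plan. This is a missing label that analysts can fill sensibly while blinded: the adjusted Cox score test decides, because the closing sentence says so and the primary analysis follows the same pattern, and the log-rank p-value accompanies the Kaplan-Meier display. Following the plan on that reading gives a valid test at about 5%. Strong assumed covariate effects took its size to 5.5% to 5.9% in simulation A, but B gave 4.2% and the rerun 4.9% (standard error 0.4 points).

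The practical residue is an ambiguous report if the two p-values straddle .05. How often that would happen cannot be pinned down. The documents give no hazard ratio, event proportion or covariate effect for this endpoint, and the two simulations differ about twofold at HR 1.35 with moderate or strong effects. Nothing follows this step in the hierarchy, so no other claim depends on it.

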5.2.2. Clinical Characteristics

Risk factors for COVID-19 progression: The number and percentage of participants with each of the protocol-defined baseline risk factors for COVID-19 progression will be summarized separately for adults and adolescents. The number of participants with ≥ 1 , ≥ 2 and ≥ 3 risk factors present at baseline will be summarized. Given differences in the definition of high risk for COVID-19 progression in this study and other mAbs that have received FDA EUA, a summary of the risk factors in the definition in the FDA EUA fact sheets may also be presented.

Duration of COVID-19 symptoms: The duration of symptom onset to randomization (defined as the time from date of onset of self-reported symptoms to the date of randomization) will be summarized with descriptive statistics and the number and percentage of participants with duration of symptoms of 0-3 days, 4-5 days, and >5 days. The duration of symptom onset to study drug administration will be summarized similarly.

COVID-19 symptoms: COVID-19 symptoms and their severity at baseline based on the symptom diary on Day 1 will be presented. The number and percentage of participants with at least 1 severe symptom, at least 1 moderate symptom and no severe symptoms, and those with only mild symptoms on Day 1 will be summarized.

COVID-19 severity: In addition, investigator-assessed COVID-19 severity (SARS-CoV-2 infection without symptoms, mild, moderate, severe, critical) will be presented as will a programmatic determination of baseline severity based on parameters collected in the eCRF and patient diary outlined in [Table 3](#). The programmatic derived COVID-19 severity will be performed at baseline and for the maximum severity through Day 29.

Table 3: Programmatic Determination of COVID-19 Severity

Protocol Defined COVID-19 Severity	Programmatic Determination
Critical COVID-19, as defined in Section 2.2.2 of the protocol	Positive local RT-PCR test at baseline, and one of the following: 
Any concomitant procedure entry of: endotracheal intubation and mechanical ventilation, high-flow oxygen (>20 L/min with $\text{FIO}_2 \geq 50\%$), noninvasive positive pressure ventilation, extracorporeal membrane oxygenationAny AE entry of: respiratory failure, shock, multisystem organ failure/dysfunction, ARDS, or acute lung injury

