- c. If a participant discontinues from the study, is lost to follow up (LFU), or dies on or before Day 29, symptom ratings will not be imputed beyond the date of discontinuation/LFU/death.
- d. If diary data are missing when a participant is not COVID-related hospitalized and remains on study (through Day 29), data will be imputed as follows:
 - The Day 1 assessment is baseline and is performed on-site prior to study drug dosing, so the assessment is not likely to be missing. If data are present for Day 1 and is missing for a sequence of consecutive days from Day 1 but with at least one subsequent score, impute the missing values through to the first available score with the value of the first available score (provided by the participant or imputed due to hospitalization). This is a conservative assumption, so that symptom improvement or resolution is less likely to be indicated early.

- If only the Day 1 assessment is missing (for a given symptom), the value will be imputed as the Day 2 value.
- For intermittent missingness during follow-up, impute the missing values as the worse of the last available value (actually provided by the participant or imputed due to hospitalization) before the missing value and the first available value (actually provided by the participant or imputed due to hospitalization) after the missing value, irrespective of length of sequence of missing values. If the last prior and the first subsequent value are equal, then symptom improvement or resolution is based on the assumption that the situation remained stable during the missing duration. If the last prior value is worse than the first subsequent one, then symptom improvement/resolution is delayed over the missing duration until improvement/resolution is confirmed. If the last prior assessment is better than the first subsequent value, then symptom improvement/resolution is reversed earlier.

- e. If a participant has no period(s) of hospitalization and all post-Day 1 data are missing (for a given symptom) or all data, including Day1, are missing (for a given symptom), the symptom will not be imputed. If all data are missing for all symptoms, the participant will be excluded in the time-to-event analyses for improvement/resolution/sustained recovery.
- f. Missing data for the questions regarding sense of taste and smell, frequency of vomiting or diarrhea, will be imputed using the values mapped to none/mild/moderate/severe.

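### The Cox test of time to sustained symptom resolution is valid but omits Day 1 symptom severity, a pre-dose covariate that would recover power if it is prognostic

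*SAP*

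**What the plan says.** SAP 5.5.3 places this endpoint last of the key secondaries: "3. Time to sustained resolution of COVID-19 symptoms through Day 29". It falls under the fixed-sequence control: "To control the overall type I error rate at .05 (2-sided), a hierarchical testing procedure will be used".

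Two comparisons are described. The first is a log-rank test: "Survival curves between ADG20 and placebo will be compared using a log-rank test stratified by age". The second is a Cox model "where the model includes age (categorical as 12-17, 18-65, and >65 years) as stratification variable and sex (categorical), baseline serostatus (categorical), baseline BMI (continuous"), followed by baseline viral load in log10 "copies/mL) as covariates. Comparison of the survival distributions will use the score test for the hazard ratio from the Cox model". Protocol 7.7 gives the same list.

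Day 1 symptom severity is collected and used elsewhere:

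- The diary runs daily from Day 1 (protocol 6.3.1.1). On its timing, Appendix F says: "The Day 1 assessment is baseline and is performed on-site prior to study drug dosing". It adds that this entry is unlikely to be missing.
- SAP 5.2.2 tabulates it: "The number and percentage of participants with at least 1 severe symptom, at least 1 moderate symptom and no severe symptoms", and those with mild symptoms only.
- SAP 3.5.1 and Table 2 use it to define sustained improvement.

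Nothing else brings it into the analysis of this endpoint. Randomization is stratified by age and country only. SAP 5.5.3.1 applies multiple imputation to the two binary key secondaries and otherwise repeats the key secondary analyses in the per-protocol set. SAP 5.6 lists mild/moderate severity as a subgroup, but the analyses it names are Estimands 1a, 2 and 3, and Appendix H defines all three on binary endpoints.

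**The concern.** The baseline state of the symptoms plausibly sets the distance to the event. Under SAP 3.5.1 and Table 2, ten of the 13 listed symptoms must be absent, while cough, fatigue and headache may remain mild. Inclusion criterion 4 requires only one qualifying sign or symptom on the day of randomization. A participant who enters with only a mild cough is already at the symptom threshold; one who enters with several severe symptoms must clear them.

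The SAP follows this logic for virology: the viral-load change models in Table 4 include the observed baseline of the same measure. The symptom model instead uses the five factors chosen for hospitalization or death.

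In a Cox model, omitting a strong prognostic covariate moves the treatment hazard ratio toward 1 and weakens the test when there is a real effect. Enrollment has stopped with about 320 participants in the primary population, against 1084 planned for the whole study, so covariate adjustment is one of the few sources of precision left.

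**Working it through.** **What can be reproduced.** The documents give no hazard ratio, event count or power for this endpoint. Their figures are for the binary primary endpoint (SAP 4.2), and these reproduce.

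- Planned size, 5% vs 1.5%, 90% power, two-sided 0.05, pooled formula: n per arm = [1.96·√(2·0.0325·0.9675) + 1.2816·√(0.05·0.95 + 0.015·0.985)]² / 0.035² = (0.4915 + 0.3198)² / 0.001225 ≈ 537.4, so 538 per arm and 1076 in total, against 1084 stated.
- Updated power, 160 per arm, 12% vs 3.6%: 80.3%, against about 80% stated.

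**Inputs for the symptom endpoint.** From the documents: about 320 participants, 1:1, follow-up to Day 29, two-sided 0.05. Assumed: the treatment hazard ratio, the proportion resolving, and the prognostic strength and distribution of severity.

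**Simulation A.** 160 per arm; exponential times rounded up to whole days and censored at Day 30; about 75–83% resolve; baseline split 25/45/30% mild only/moderate/severe; conditional hazard ratio 1.35; 1500 trials per setting. The Cox score test adjusted for sex, serostatus, BMI and viral load is compared with the same test plus three-level severity.

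| Resolution hazard multiplied per severity step by | Power without severity | Power with severity | Gain (points) |
|---|---|---|---|
| 0.74 | 61.9% | 64.0% | 2.1 |
| 0.61 | 57.3% | 63.6% | 6.3 |
| 0.50 | 48.4% | 62.3% | 13.9 |
| 0.41 | 45.5% | 61.9% | 16.4 |

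At a hazard ratio of 1, rejection was 3.7–6.0% without severity and 3.0–6.1% with it.

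**Simulation B.** n = 320; exponential times censored at Day 29; conditional hazard ratio 1.4; one standardized severity score; Wald test; 2000 trials per setting. No other covariates are simulated, so the severity effect should be read as what remains after them.

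| Severity hazard ratio per SD | Resolving | Estimated HR, without → with | Power, without → with | Gain (points) |
|---|---|---|---|---|
| 1.22 | 70% | 1.39 → 1.40 | 69.7% → 71.0% | 1.3 |
| 1.49 | 70% | 1.37 → 1.41 | 65.2% → 72.3% | 7.1 |
| 2.01 | 70% | 1.32 → 1.41 | 55.0% → 71.6% | 16.6 |
| 1.22 | 50% | 1.40 → 1.41 | 55.2% → 56.3% | 1.1 |
| 1.49 | 50% | 1.37 → 1.40 | 50.1% → 54.9% | 4.8 |
| 2.01 | 50% | 1.34 → 1.40 | 43.5% → 54.1% | 10.6 |

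At a hazard ratio of 1, rejection was 4.0–5.2% without severity and 4.4–5.2% with it.

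Cross-check by Schoenfeld's formula with no severity effect: 70% of 320 is 224 events; √224/2 · ln 1.4 − 1.96 = 2.518 − 1.96 = 0.558, giving 71.2% power against 70.7% simulated.

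**In events.** Power depends on the square of (1.96 + z for the power). For the moderate cases, ((1.96 + 0.348)/(1.96 + 0.184))² = 1.16 in A and ((1.96 + 0.592)/(1.96 + 0.391))² = 1.18 in B. A moderately prognostic covariate is therefore worth about 16–18% more events.

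**The case against.** The planned analysis contains no error. It is pre-specified, identical in both documents and uses the same factors as the other controlled tests. It holds its type I error, and it contradicts no stated power for this endpoint because none is stated. All of that stands.

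The size is also open. The severity effect, its distribution, the treatment hazard ratio and the resolution rate are all assumed. If severity is correlated with viral load or serostatus, which are already in the model, the gain shrinks. At the weak end, 1–2 points is close to simulation error. Part of the shift in the hazard ratio is non-collapsibility: adding the covariate changes which conditional hazard ratio is estimated. These limits stand too, though they do not remove the loss of power when severity is prognostic.

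The grouping in SAP 5.2.2 cannot be used as it is. It describes a table based on the diary, which includes taste and smell; the endpoint excludes both. Appendix F maps total loss of either to severe and partial loss to an undivided mild/moderate class. The grouping has no level for someone without symptoms.

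Stratifying the log-rank test by severity as well as age would make nine strata in about 320 people, which was not tested. This is a reason to use a covariate and leave the log-rank test alone.

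Finally, protocol 7.3 promises the key secondary analyses within subgroups. Even if that is read to include this endpoint, subgroup estimates do not replace adjustment.

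**Conclusion.** The point holds as a conditional loss of efficiency in a valid test. With about 70% or more resolving and an assumed hazard ratio of 1.35–1.4, the omission costs about 1–2 power points if severity is weakly prognostic, 6–7 if moderately and 14–17 if strongly. With 50% resolving, the costs in simulation B are about 1, 5 and 11 points. The conclusion needs a true effect of ADG20 on resolution and severity that is prognostic beyond age, sex, serostatus, BMI and viral load. It also treats the Cox score test, rather than the log-rank test, as the decision test.

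A reader might infer more than the documents support:

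- *That attenuation and lost power are established.* No document figure gives the prognostic strength, so only the direction under the stated conditions is shown.
- *That false-positive risk is raised.* Both simulations show no inflation.
- *That every participant has the Day 1 value.* Appendix F calls missing entries unlikely and has rules for them.
- *That three confirmatory analyses are weakened.* Only resolution is alpha-controlled, and it is reached only if the earlier tests succeed. Sustained recovery is a descriptive secondary analysis and sustained improvement is exploratory.

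**What to change.** Before unblinding, add one pre-specified Day 1 symptom severity covariate to the Cox model in SAP 5.5.3 and protocol 7.7, and for consistency in SAP 5.5.6.2 and 5.5.6.3.

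- **Definition.** Use only the 13 endpoint symptoms, excluding taste and smell: for example, worst severity as none/mild/moderate/severe, or a total score. Define the level for participants with none of these symptoms.
- **Missing Day 1 entry.** Use a rule based on pre-dose data, such as the average of observed baseline values that SAP 5.5.1 applies to BMI and viral load. Do not use Appendix F's Day 2 substitution for the covariate, because for dosed participants Day 2 is after dosing.
- **Form.** Enter it as a covariate, not as a further stratum, and keep the log-rank test stratified by age.
- **Record.** SAP section 7 reports no changes from the protocol. If protocol 7.7 is not amended, note the change there.

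The cost is one added definition and one model term, with no new data. The hazard ratio also becomes conditional on baseline severity, which the report should say. SAP 3.2 already provides for blinded decisions and sign-off before unblinding.
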